10.6. Archiving

It is the responsibility of the PI to ensure all essential trial documentation and source documents (e.g. signed ICFs, ISFs, Pharmacy Files, participants' hospital notes, CRFs etc.) at their site are securely retained for at least 10 years. Archiving will be authorised by BCTU on behalf of UoB following submission of the end of trial report. No documents should be destroyed without prior approval from the Trial Office.

Prior to long term archiving, the TMF will be stored at the Trial Office under controlled conditions. Long-term offsite data archiving facilities will be considered for storage after this time; data will be stored for at least 10 years. BCTU has standard processes for both hard copy and computer database legacy archiving.

11. QUALITY CONTROL AND QUALITY ASSURANCE

11.1. Site Set-up and Initiation

All PIs will be asked to sign the necessary agreements including a **Site Signature & Delegation Log** between the PI and BCTU, and supply an up to date signed CV and GCP certificate to the Trial Office. All site staff who are performing trial specific tasks are required to sign the Site Signature and Delegation Log, which details which tasks have been delegated to them by the PI.

Prior to commencing recruitment, each recruiting site will undergo a process of initiation, either a meeting or a teleconference, at which key members of the site research team are required to attend, covering aspects of the trial design, protocol procedures, adverse event reporting, collection and reporting of data and record keeping. Sites will be provided with an ISF containing essential documentation, instructions, and other documentation required for the conduct of the trial. The Trial Office must be informed immediately of any change in the site research team.

11.2.Monitoring

The monitoring requirements for this trial have been developed following trial specific risk assessment by BCTU and as documented in the monitoring plan.

11.3. Onsite Monitoring

For this trial we will monitor all sites in accordance with the trial Risk Assessment and Monitoring Plan. Investigators will allow the STOP-APE trial staff access to source documents as requested. The monitoring will be conducted by BCTU staff.

11.4.Central Monitoring

Trials staff will check incoming ICFs and CRFs for compliance with the protocol, data consistency, missing data and timing at a frequency and intensity determined by the **Data Management Plan**. Sites will be sent DCFs requesting missing data or clarification of inconsistencies or discrepancies.

Sites will be requested to send in copies of signed ICFs and other documentation for central review for all participants providing explicit consent. This will be detailed in the Monitoring Plan.

11.5. Audit and Inspection

The Investigator will permit trial-related monitoring, audits, ethical review, and regulatory inspection(s) at their site, providing direct access to source data/documents. The investigator will comply with these visits and any required follow up. Sites are also requested to notify the Trial Office of any relevant inspections.

11.6. Notification of Serious Breaches

Sites may be suspended from further recruitment in the event of serious and persistent non-compliance with the protocol and/or GCP, and/or poor recruitment. Any major problems identified may be reported to the Trial Management Group and Trial Steering Committee, and the REC. This includes reporting serious breaches of GCP and/or the trial protocol to the REC. A copy is sent to the University of Birmingham Clinical Research Compliance Team at the time of reporting to the REC and/or relevant regulatory bodies.

The Sponsor is responsible for notifying the REC of any serious breach of the conditions and principles of GCP in connection with that trial or the protocol relating to that trial. Sites are therefore requested to notify the Trials Office of any suspected trial-related serious breach of GCP and/or the trial protocol. Where the Trials Office is investigating whether or not a serious breach has occurred sites are also requested to cooperate with the Trials Office in providing sufficient information to report the breach to the REC where required and in undertaking any corrective and/or preventive action.

12. END OF TRIAL DEFINITION

The end of trial will be 6 months after the last data capture, including DCFs. This will allow sufficient time for the completion of protocol procedures, data collection and data input. The Trial Office will notify the REC and RGT within 90 days of the end of trial. Where the trial has terminated early, the Trials Office will inform the REC within 15 days of the end of trial. The Trials Office will provide the REC and RGT with a summary of the clinical trial report within 12 months of the end of trial.

13. STATISTICAL CONSIDERATIONS

13.1.Sample Size

The trial is powered on the superiority for bleeding events and non-inferiority for recurrent VTE.

Superiority for bleeding events:

With 90% power and two-sided alpha=0.05, to detect a decrease in major bleeding or CRNMB from 7% (based on a meta-analysis of DOAC RCTs)² in the anticoagulation group to 3% in the no anticoagulation group using a two-sample proportions test, 1244 patients (622 per group) are required.

Non-inferiority for recurrent VTE:

We also aim to detect whether no anticoagulation is non-inferior to treatment with anticoagulation regarding VTE recurrence. With 90% power, and a one sided alpha=0.025, a VTE recurrence rate of 2% with anticoagulation (also based on the DOAC RCT meta-analysis)² and a non-inferiority margin of 2.5%, 1,320 patients would be needed. Taking the largest of the two sample sizes computed (i.e. sample size for non-inferiority), allowing for 10% attrition, a total of 1466 patients (733 per arm) would be needed. Sample size calculations were performed using Stata 13.

13.2. Analysis of Outcome Measures

A separate Statistical Analysis Plan will be produced and will provide a more comprehensive description of the planned statistical analyses. A brief outline of these analyses is given below.

The primary comparison groups will be composed of those treated without anticoagulation versus those treated with anticoagulation. All analyses will be based on the intention to treat principle as well as the per-protocol, with per-protocol set being patients with confirmed SSPE based on CTPA review.

For all outcome measures, appropriate summary statistics will be presented by group (e.g. proportions/percentages, mean/standard deviation or median/interquartile range). Intervention effects will be adjusted for the minimisation variables listed in section 6.2 and baseline scores where possible. 95% confidence intervals (CI) and p-values will be presented for all outcomes. No adjustment for multiple comparisons will be made.

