If following central thoracic radiologist review of the participants' CTPA or CT Thorax, it is found that a randomised participant has a PE affecting a larger vessel or no SSPE is present, providing their continuing consent they should continue to be followed up as part of the trial. All patients will be analysed for the primary outcome, and as per protocol analysis will be undertaken on patients with a confirmed diagnosis of ISSPE.

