13.2.2. Secondary Outcome Measures

The secondary outcomes are a combination of binary data, continuous data and count data.

Binary outcomes:

The secondary outcomes that are binary (e.g. VTE related death) will be analysed using the same methods described for the co-primary outcomes (see Section 13.2.1).

Continuous outcomes:

For those secondary outcomes that are continuous (e.g. EQ-5D-5L), linear regression methods will be used for analysis. Results will be presented as adjusted mean difference. If data is found to be not normally distributed, then transformation of the data to get it into a normally distributed form (e.g. log-transformation) will be conducted prior to any analysis.

Count data outcomes:

For those secondary outcomes that are count data types (e.g. Hospitalisations, Unscheduled visits), Poisson regression model will be used for analysis. Time will be used as an offset in the model. Results will be presented as an adjusted incidence rate ratio.

Reclassification rates from thoracic radiologist review:

Reclassification rates for all recruited patients will be calculated with 95% binomial exact confidence intervals for (a) no SSPE and (b) PE requiring anticoagulation as the risks arising from misclassification are different in these patients' populations with implications for implementation as NHS practice does not currently include radiological review. These rates will be analysed without any adjustment. These reclassification rates by trial arm will be included in the table of baseline characteristics. Variation between centres will be described anonymously as understanding centre contribution to reclassification rates may be relevant to intervention implementation. Radiological review of the SSPE diagnosis by the acute reporting radiologist is required as a safety check to ensure randomised patients receive appropriate treatment, that is, anticoagulation of patients with no SSPE randomised to anticoagulation can be halted and anticoagulation of patients with PE which requires it can be initiated.

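### The set called per-protocol is selected on imaging alone, so neither planned analysis set addresses non-adherence in the non-inferiority comparison

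*Protocol*

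**What the plan says.** Section 13.2 bases all analyses on intention to treat and also on a per-protocol set, "with per-protocol set being patients with confirmed SSPE based on CTPA review". Section 8.5 repeats the definition: "as per protocol analysis will be undertaken on patients with a confirmed diagnosis of ISSPE". Neither place sets a condition on adherence to the allocated strategy.

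Just before naming intention to treat, section 13.2 says: "The primary comparison groups will be composed of those treated without anticoagulation versus those treated with anticoagulation".

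The protocol foresees departures from allocation. Section 8.5 has a status category for a participant who gives up the allocated strategy but agrees to further follow-up. Section 7.3 accepts that pregnancy may lead to a change of arm. Section 7.3 also describes treatment changes after central review of the scan, and section 13.2.2 explains them: "anticoagulation of patients with no SSPE randomised to anticoagulation can be halted and anticoagulation of patients with PE which requires it can be initiated". Anticoagulant starts, stops and changes are recorded at 4, 12 and 24 weeks (sections 8.3 and 8.4).

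**The concern.** A per-protocol set is normally run beside intention to treat in a non-inferiority trial because departures from allocation make the arms more alike, and similarity is what the trial sets out to show. The set defined here cannot do that job. It selects patients on the baseline scan and then analyses them as allocated. A participant with confirmed subsegmental embolism who leaves the allocated strategy is counted identically in both sets, so agreement between the two says nothing about non-adherence.

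The trial is open-label and withholds standard care. If some of the withholding arm is in fact anticoagulated, the observed difference in recurrent VTE shrinks. The chance of declaring non-inferiority when the full strategy reaches the margin then exceeds the nominal 2.5%.

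The sentence defining the groups by treatment received adds a second problem. Once anyone crosses over, groups formed by treatment and groups formed by randomisation contain different people.

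**Working it through.** **Inputs from protocol section 13.1.** "With 90% power, and a one sided alpha=0.025"; "a VTE recurrence rate of 2% with anticoagulation"; "a non-inferiority margin of 2.5%, 1,320 patients would be needed"; "allowing for 10% attrition, a total of 1466 patients (733 per arm) would be needed". The margin is read as 2.5 percentage points, since that reading reproduces the stated sample size.

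**Reproducing the plan's figure.** With 2% in both arms and 660 per arm:
- SE = √(2 × 0.02 × 0.98 / 660) = 0.00771
- power = Φ(0.025/0.00771 − 1.96) = Φ(1.284) = 90.0%

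So 660 per arm, 1,320 in total, is confirmed. 1,320/0.9 = 1,466.7, against 1,466 stated.

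**Assumptions not in the documents.**
- A fraction c of the withholding arm crosses over, with c = 10% or 20%.
- Full adherence gives 2% against 4.5%, so the true difference equals the margin.
- A participant who crosses over has the risk of the strategy received for the whole 3 months. Later crossover would dilute less.

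**Formulas.**
- p_T = (1 − c) × 0.045 + c × 0.02, and p_C = 0.02
- SE = √{[p_T(1 − p_T) + p_C(1 − p_C)]/n}
- false non-inferiority = Φ[(0.025 − (p_T − p_C))/SE − 1.96]

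**Worked cases, n = 660.**
- c = 10%: p_T = 0.0425, difference 0.0225, SE = 0.00956. Φ(0.262 − 1.96) = Φ(−1.698) = 4.5%.
- c = 20%: p_T = 0.040, difference 0.020, SE = 0.00937. Φ(0.533 − 1.96) = Φ(−1.427) = 7.7%.

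The second sample size, 594 = 0.9 × 660, is the confirmed set if 10% are dropped on review and not replaced. Section 1.1 cites 10% from some case series; it is not a forecast for this trial.

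| Crossover | 660 per arm | 594 per arm |
|---|---|---|
| None | 2.5% | 2.5% |
| 10%, withholding arm | 4.5% | 4.3% |
| 20%, withholding arm | 7.7% | 7.3% |
| 10%, each arm | 7.4% | 7.0% |

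**Check by simulation** (400,000 binomial trials per case, Wald 95% interval). With 660 per arm: 3.0% without crossover, 5.3% at 10% and 8.9% at 20% in the withholding arm. With 594: 3.0%, 5.1% and 8.4%. The Wald interval is slightly liberal at these low rates even without crossover. The rise due to crossover is similar to that in the formula.

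**Which departures stay in which set.** Changes triggered by central review occur in patients with a larger-vessel embolism or no embolism. The confirmed set excludes them. Departures by participant choice, clinician choice or pregnancy among confirmed patients remain in both sets.

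**The case against.** Several points on the other side stand.

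- A reader might infer that the per-protocol set keeps every crossover. It does not: the treatment changes that the protocol itself triggers fall in patients whom the set excludes.
- A reader might infer that no planned analysis guards against reclassification. The confirmed set does exactly that. Section 6.2 also bars randomisation when an adverse review arrives first.
- A reader might infer that power in the confirmed set falls to 86.8%, the value at 594 per arm. Section 3.3.1 answers this by applying the recruitment target to patients with true subsegmental embolism.
- The direction of bias is not certain. Section 8.2.1 counts an untested suspected DVT or PE as confirmed if it changed therapeutic anticoagulation, so some withholding-arm starts become events. At 10% crossover the dilution is 0.25 points, or 0.0025 × 660 = 1.65 events; about two extra events counted this way would cancel it.
- No crossover rate is stated, and patients who decline no treatment are counted before randomisation (section 2.1).
- Section 13.2 calls itself an outline. Which set carries the claim, or whether both must agree, is commonly settled in the SAP, which is not shown. Its absence here is not an error.
- The intention-to-treat sentence follows directly, so the wording on treatment received may only be loose.

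None of this supplies an adherence criterion. The protocol fixes the definition in two places, so it is not a detail left open.

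**Conclusion.** The point holds in a limited form. The set labelled per-protocol is a modified intention-to-treat set. It deals with misdiagnosis and leaves non-adherence among confirmed patients untouched in both planned analyses. The description of the comparison groups conflicts with intention to treat.

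False non-inferiority would be about 4.5% to 7.7% with 660 per arm, or 4.3% to 7.3% with 594, against 2.5% nominal. This rests on an assumed withholding-arm crossover of 10% to 20%, a true difference at the margin, and crossover acting from randomisation. The endpoint rule in section 8.2.1 may reduce it by an unknown amount. The documents do not show that crossover will be common, nor that non-inferiority may be claimed from intention to treat alone. This should be fixed, but it does not invalidate the design.

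**What to change.** 1. In sections 13.2 and 8.5, rename the present set *confirmed ISSPE (modified ITT)*.
2. Add a per-protocol set: confirmed ISSPE plus adherence to the allocated strategy up to 3 months or the first primary event, whichever comes first. Use the 4- and 12-week medication checks. An anticoagulant start that itself counts as a VTE under section 8.2.1 should be handled as an event and not as non-adherence.
3. State that the non-inferiority conclusion must be consistent in the intention-to-treat and per-protocol sets.
4. In section 13.2, define the comparison groups as those *randomised to* each strategy.

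The cost is wording and one further analysis on data already collected.

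The downside is real. If 10% are reclassified and 10% of the rest are non-adherent, with no extra recruitment, 660 × 0.9 × 0.9 ≈ 535 per arm remain. Power is then Φ(0.025/√(0.0392/535) − 1.96) = Φ(0.96), about 83%. Requiring consistency with intention to treat cannot raise it. The extra recruitment foreseen in section 3.3.1 would recover some of the loss. The set also conditions on behaviour after randomisation and returns the error to about 2.5% only if non-adherence is unrelated to risk. It should be read alongside intention to treat and not replace it.

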13.2.1. Primary Outcome Measure

The multiple (joint) primary outcomes are both binary outcomes (i.e. yes/no) and will be analysed using a generalised linear model (with binomial distribution and log link), adjusting for minimisation variables listed in Section 6.2. Treatment effects will be expressed as adjusted risk ratios with 95% CIs. If the model does not converge, then a Poisson regression models with log link and with robust variance estimation will be used (28). We will also present the adjusted risk difference alongside the adjusted risk ratio and so to estimate the adjusted risk difference, a generalised linear model (with binomial distribution and identity link) will be fitted adjusting for minimisation variables listed in Section 6.2.

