6.4. Randomisation

6.4.1. Randomisation Methodology

Participants will be randomised by computer at the level of the individual in a 1:1 ratio to either intervention (withhold anticoagulation treatment) or control (full dose anticoagulation treatment as standard of care) arm.

A minimisation algorithm will be used within the online randomisation system to ensure balance in the treatment allocation over the following variables:

- Age (<50, 50-70, >70 years)
- Cancer (Yes/No)
- Clinically suspected or confirmed COVID-19 (Yes/No)
- Type of SSPE (Symptomatic / Incidental)
- Previous clinically relevant bleeding as defined by the International Society on Thrombosis and Haemostasis (ISTH) (Yes/No)
- Randomising site

A 'random element' will be included in the minimisation algorithm, so that each participant has a probability (unspecified here), of being randomised to the opposite treatment that they would have otherwise received.

Full details of the randomisation specification will be stored in a confidential document at the Trial Office.

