8.2.1. Multiple (joint) Primary Outcomes

Composite of recurrent VTE (nonfatal) and/or VTE related death (primary safety outcome) and clinically relevant bleeding, which is a composite of major and clinically relevant non-major bleeding (CRNMB) (primary efficacy outcome) within 3 months post-randomisation.

The following primary outcome definitions will be used by the CIAC:

VTE recurrence

Composite of nonfatal VTE (PE or DVT) recurrence and/or VTE-related death.

PE recurrence

Suspected (new or recurrent) PE with one of the following findings:

- A new intraluminal filling defect in a subsegmental or more proximal pulmonary artery on CTPA or CT thorax with IV contrast
- An extension of an existing subsegmental pulmonary embolism on CTPA or CT thorax with IV contrast
- A new perfusion defect of at least 75% of a segment with a local normal ventilation result (high-probability) on ventilation/perfusion lung scan

 Symptoms suggestive of PE but with an inconclusive CTPA, CT thorax with IV contrast or ventilation/perfusion scan for PE, and with evidence of a new DVT in the lower extremities by compression ultrasound or venography.

DVT recurrence

Suspected (recurrent) DVT with one of the following findings:

- abnormal compression ultrasound
- an intraluminal filling defect on venography (CT/MR/invasive)

Objective testing for PE/DVT recurrence will be encouraged, but in the absence of objective testing, a suspected episode of DVT or PE will be considered as confirmed if it led to a change in anticoagulant treatment at therapeutic dosages.

VTE-related death

- PE based on objective diagnostic testing, autopsy, or
- Death which cannot be attributed to a documented cause and for which PE/DVT cannot be ruled out (unexplained death).

Clinically relevant bleeding

Composite of major bleeding and clinically relevant non major bleeding (CRNMB).

Major bleeding

Is defined by ISTH criteria:

- 1. Fatal bleeding, and/or
- 2. Symptomatic bleeding in a critical area or organ, such as intracranial, intraspinal, intraocular, retroperitoneal, intra-articular or pericardial, or intramuscular with compartment syndrome, and/or
- 3. Bleeding causing a fall in haemoglobin level of 20g L⁻¹ (1.24 mmol L⁻¹) or more, or leading to transfusion of two or more units of whole blood or red cells.

Clinically relevant non-major bleeding (CRNMB)

Is defined by ISTH criteria:

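### Recurrent VTE: the non-inferiority margin is an absolute risk difference, but Section 13.2.1 leads with a risk ratio, names no deciding measure, and gives a convergence fallback only on the ratio scale

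*Protocol*

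**What the plan says.** **Sample size (Protocol, Section 13.1).** The non-inferiority calculation uses "With 90% power, and a one sided alpha=0.025", "a VTE recurrence rate of 2% with anticoagulation" and "a non-inferiority margin of 2.5%, 1,320 patients would be needed". The text does not name the scale of the margin. The final target follows as "allowing for 10% attrition, a total of 1466 patients (733 per arm) would be needed".

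**Primary analysis (Protocol, Section 13.2.1).** Both joint primary outcomes, assessed "within 3 months post-randomisation" (Section 8.2.1), are modelled by a binomial GLM with a log link, adjusted for the minimisation variables: "Treatment effects will be expressed as adjusted risk ratios with 95% CIs". If that model does not converge, a Poisson model with log link and robust variance replaces it. The section then adds: "We will also present the adjusted risk difference alongside the adjusted risk ratio". That estimate comes from a binomial model with identity link and the same adjustment. No fallback is given for it.

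**Adjustment variables.** Section 13.2.1 points to Section 6.2 for these, but the list is in Section 6.4.1. It includes the randomising site, and Section 3.2 plans about 50 sites.

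No section states the margin as a ratio, or says which interval is compared with 2.5%.

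**The concern.** Recurrent VTE is the primary safety outcome, and the trial asks of it a yes/no non-inferiority question. That question has an answer only when an interval and a margin are on the same scale. The measure that Section 13.2.1 puts first, and protects with a fallback, is on a different scale from the margin. The measure on the right scale comes second and has no fallback.

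Two things are at stake. First, with no named deciding measure, the same data can read as a clear success on one scale and as unsettled on the other. Second, if the identity-link model fails, the analysis that the protocol still prescribes is a risk ratio. Someone would then have to choose a ratio margin, or a new risk-difference method, after the data are available.

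**Working it through.** **1. Reproduce the plan's figure.** Inputs from Section 13.1: 2% with anticoagulation, margin 0.025, one-sided alpha 0.025 (z = 1.960), power 90% (z = 1.2816). Allocation is 1:1 (Section 6.4.1: "Participants will be randomised by computer at the level of the individual in a 1:1 ratio"). The true rate under withholding is not stated; I assume it is also 2%.

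Risk difference, unpooled variance:

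n per arm = (1.960 + 1.2816)² × 2 × 0.02 × 0.98 / 0.025² = 659.03, so 660 per arm and 1,320 in total. This matches exactly. With 10% attrition, 1,320 / 0.9 = 1,466.7, against a stated 1,466.

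Other readings of 2.5% do not give 1,320. As a ratio margin of 2.5, about 1,227 per arm would be needed. As a ratio margin of 1.025, it would be about 1.7 million per arm. The margin is therefore an absolute 2.5 points, from 2.0% to 4.5%.

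**2. Power on the scale of the margin.** SE = √(2 × 0.02 × 0.98 / 660) = 0.00771. Power = Φ(0.025 / 0.00771 − 1.960) = 90.0% (89.7% by simulation). With all 733 per arm analysed it is 92.8%.

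**3. What a ratio reading would do.** A risk ratio has no fixed equivalent of a 2.5-point margin. The equivalent is (p + 0.025) / p, where p is the control rate: 3.5 at p = 1%, 2.25 at 2%, 1.83 at 3%. Suppose 2.25 were adopted. Then SE(log RR) = √(2 × 0.98 / (660 × 0.02)) = 0.385, and power = Φ(0.811 / 0.385 − 1.960) = 55.7% (54.6% by simulation). This is a hypothetical rule, because the protocol sets no ratio margin.

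**4. Two possible results, 660 per arm, unadjusted Wald intervals.**

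| Events, control / withhold | Risk difference, points (upper 95% limit) | Risk ratio (upper 95% limit) |
|---|---|---|
| 13 / 16 | 0.45 (2.04) | 1.23 (2.54) |
| 7 / 14 | 1.06 (2.41) | 2.00 (4.92) |

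Both results meet the 2.5-point margin. Neither risk ratio yields a verdict without a ratio margin. In the first, the upper limit exceeds 2.25. In the second, a report led by the ratio would show a doubling of VTE in a trial that met its margin.

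**5. Is the identity-link model likely to fit?** Expected events are 0.02 × 1,320 = 26.4, or 26.4 / 50 ≈ 0.5 per site. With 26 events, at least 50 − 26 = 24 of 50 sites would have none. Fitted risks in those sites are pushed to zero, the boundary where an identity-link binomial model breaks down. In a small simulation with about 26 events and assumed covariate prevalences, the model gave a valid fit in 3 of 40 runs without site and in 0 of 40 with 50 site terms. The exact rates depend on the assumed prevalences, but the direction is clear.

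**The case against.** The strongest reply is that Section 13.2.1 already plans the right estimate. It commits to an adjusted risk difference for both primary outcomes and names its model, and Section 13.2 promises 95% CIs for all outcomes. The upper limit of a two-sided 95% CI corresponds to the one-sided 0.025 test and can be read directly against 2.5 points. Reporting relative and absolute effects together is good practice. Which limit meets which margin is commonly written in the SAP, and the protocol calls its own account a brief outline.

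Much of this stands. Sections 13.1 and 13.2.1 do not flatly contradict each other, and a missing decision sentence alone could be left to the SAP.

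A reader might go further and infer that the primary analysis cannot be tested against the margin at all, or that the trial really has about 56% power. The documents support neither. The risk difference is planned, and its power is 90%. The 56% needs a ratio margin of 2.25 that appears nowhere in the protocol.

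The reply does not cover what the protocol itself fixes: a ratio as the leading measure for both outcomes, and a fallback that exists only for the ratio. The planned risk difference helps only if its model fits, and step 5 shows that this is doubtful.

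**Conclusion.** The point holds as a mismatch of scale and an unprotected model, not as a fault in the sample size. The margin is an absolute 2.5 percentage points, and power is 90% at 660 per arm on that scale. Section 13.2.1 gives priority and the only fallback to a measure that cannot be compared with it, and leaves the deciding measure unnamed. The identity-link model will probably fail with about 26 events and about 50 sites, and the protocol would then prescribe only a risk ratio for a non-inferiority question posed on the difference scale.

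This assumes a true 2% rate in both arms, about 50 sites each entered as a term in the model, and the covariate prevalences assumed in the simulation. Treating site as a random effect or omitting it would ease the problem, but the few runs without site also mostly failed. The SAP, which is not available here, may already settle the matter; if so, the protocol should be brought into line with it.

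**What to change.** In Section 13.2.1:

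- Make the adjusted risk difference (withhold minus anticoagulate) the primary measure for recurrent VTE.
- Declare non-inferiority if the upper limit of its two-sided 95% CI is below 2.5 percentage points. In Section 13.1, write the margin as percentage points.
- Add a fallback that stays on the risk-difference scale, for example a standardised marginal risk difference, or a robust-variance identity-link model with fewer covariates. State how site is handled.
- Keep the risk ratio as supportive for recurrent VTE.
- Correct the cross-reference for the minimisation variables to Section 6.4.1.

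The cost is protocol and SAP wording and a little more analysis work. No extra patients or data are needed, and the sample size stays as it is.

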3.2. Trial Setting

Participants will be recruited from approximately 50 trial sites from secondary care clinical settings of emergency departments, ambulatory care and acute medical units within NHS hospitals in the UK. The recruitment rates will be assessed during the pilot phase and additional sites will be recruited if required (see section 2.1).

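### The adjusted risk difference, the only planned estimate on the scale of the 2.5% margin, comes from an identity-link binomial model that the expected event counts cannot support, with no fallback on that scale

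*Protocol*

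**What the plan says.** Protocol 13.1 sizes the non-inferiority comparison "With 90% power, and a one sided alpha=0.025, a VTE recurrence rate of 2% with anticoagulation" and "a non-inferiority margin of 2.5%, 1,320 patients would be needed"; "allowing for 10% attrition, a total of 1466 patients (733 per arm) would be needed".

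Protocol 13.2.1 analyses both joint primary outcomes with a log-link binomial model that gives an adjusted risk ratio. If that model does not converge, a log-link Poisson model with robust variance replaces it. The adjusted risk difference is shown beside the ratio and comes from a separate "generalised linear model (with binomial distribution and identity link) will be fitted adjusting for minimisation variables listed in Section 6.2". No alternative is named for this second model.

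Section 6.2 is the registration process. The minimisation list is in 6.4.1: age in three bands, cancer, COVID-19, type of SSPE, previous clinically relevant bleeding, and "Randomising site". Section 3.2 plans "approximately 50 trial sites". Section 13.2.3 leaves centre out of the subgroup analyses; 13.2.1 contains no such exclusion for the main models.

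Two further statements matter. Section 13.2 makes adjustment subject to a general proviso of feasibility and defers fuller description to a separate SAP. Section 13.2.2 says that binary secondary outcomes "will be analysed using the same methods described for the co-primary outcomes".

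**The concern.** A margin of 2.5 percentage points can be compared directly only with a risk difference and its upper confidence limit. A risk ratio cannot be held against it without a further assumption about the control risk. The identity-link model is therefore the one planned route to a non-inferiority conclusion.

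That model requires every fitted risk to lie between 0 and 1 while the covariate effects add up on the probability scale. With risks near 2% and many covariates, the constraint binds. If the model fails and nothing is named in its place, the estimator for the non-inferiority question is selected after the data have been seen, in an open-label trial. A second hazard is software that stops quietly at the boundary and prints an interval that means nothing.

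**Working it through.** **1. Scale of the margin.** With 2% in both arms, one-sided alpha 0.025, 90% power and margin d = 0.025:

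n per arm = (1.960 + 1.282)² × 2 × 0.02 × 0.98 / 0.025² = 10.507 × 62.72 = 659.02, rounded up to 660, so 1,320 in total.

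This is the protocol's figure, so the margin is an absolute difference. Likewise 1,320 / 0.9 = 1,466.7, against the stated 1,466.

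**2. Events and parameters.**
- Expected VTE events: 1,320 × 0.02 = 26.4. With all 1,466 analysed, 29.3. With the intervention arm at 4.5%, 660 × 0.02 + 660 × 0.045 = 42.9.
- Parameters with site as indicators: intercept 1 + treatment 1 + age 2 + binary factors 4 + sites 49 = 57.
- Events per parameter: 26.4 / 57 = 0.46.

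**3. Sites without an event.** With 50 equal sites of 26.4 patients, the chance that a site has none is 0.98^26.4 = 0.587, so 50 × 0.587 = 29 sites are expected to have none (28 at N = 1,466). With unequal simulated sites the average was 31, holding 48% of patients. The chance that no site is event-free is (1 − 0.587)^50, about 7 × 10⁻²⁰.

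**4. Why one event-free site is enough.** Under the identity link, the derivative of the log-likelihood with respect to the term for an event-free site is −Σ 1/(1 − μᵢ) over its patients. This is negative everywhere, so the likelihood rises as the term falls until some fitted risk in that site reaches 0. No interior maximum exists, and the usual Wald interval has no basis. This step does not depend on software, site sizes or factor prevalences. It does depend on site being a fixed indicator.

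**5. Simulation with site indicators.** N = 1,320, 50 unequal sites, Fisher scoring with step-halving and fitted risks kept strictly inside (0, 1):

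| Scenario | Clean interior fits |
|---|---|
| VTE 2% v 2% | 0 of 200 |
| VTE 2% v 4.5% | 0 of 200 |
| Bleeding 7% v 3% | 0 of 200 |

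For VTE at 2% v 2%, 153 runs hit the iteration limit, 43 stopped at the boundary and 4 failed outright. A routine that clips fitted risks reported convergence in 92% to 97% of VTE trials, but with a risk difference near 0 and a standard error of about 5 × 10⁻⁹ to 7 × 10⁻⁹.

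**6. Same model without site.** Clean fits for VTE, 200 runs each. Outcomes were generated with no covariate effects; the prevalences of the four binary factors are assumptions.

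| Assumed prevalences (cancer / COVID-19 / incidental / prior bleeding) | N = 1,320 | N = 1,466 |
|---|---|---|
| 10 / 10 / 25 / 5% | 14 | 24 |
| 20 / 20 / 35 / 15% | 27 | 34 |
| 40 / 40 / 50 / 40% | 36 | 41 |

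A separate set of runs at N = 1,320 with the lowest prevalences gave 11 of 200 at 2% v 2% and 20 of 200 at 2% v 4.5%. The overall range is therefore about 6% to 20%. For bleeding without site it was 50 of 200. With treatment alone, the identity-link model fitted in 200 of 200.

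**7. An alternative that works.** Standardisation from a logistic model on treatment and the patient-level factors gave a finite risk difference and standard error in 200 of 200 runs in each scenario. For VTE at 2% v 2% the mean standard error was 0.0077 and the empirical SD 0.0074. The simple unadjusted value is √(2 × 0.02 × 0.98 / 660) = 0.0077, so nothing is lost in precision.

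**The case against.** The strongest reply is that a protocol outline need not settle convergence rules or the coding of site. Section 13.2 defers detail to the SAP and adjusts only as far as feasible. The SAP may already name a replacement or treat site as a random effect.

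Part of this stands. The protocol does not say how site enters, so the 57 parameters and the 0 of 200 results are conditional on fixed indicators. A plain generalised linear model points that way but does not settle it. A reader might also infer that analysts will inevitably choose an estimator after seeing the data. The documents do not support that, because the SAP is unseen.

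The rest does not stand. Section 13.2.1 itself fixes the distribution, the link and the adjustment set, so this is a stated model that fails rather than a detail left open. The authors foresaw non-convergence and gave a remedy, but only on the ratio scale. The feasibility proviso gives no rule for what is dropped or when. Removing site by any route still leaves a model that rarely fits.

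It can also be said that the protocol never states that the risk difference decides non-inferiority; it is presented beside the ratio. That is correct. Its decisive role is inferred from the scale of the margin and from the absence of any other planned estimate on that scale.

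**Conclusion.** The concern holds in conditional form. With site as fixed indicators, the stated risk-difference model has no valid interior fit or Wald interval at the planned VTE event count; this follows analytically once a single site is event-free, and about 29 to 31 are expected to be. Without site, about 6% to 20% of simulated VTE trials fitted cleanly. That range depends on the assumed prevalences and on the fitting algorithm.

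Two stronger readings should be resisted. One is that the model simply will not run: some software will report a fit, although with a standard error that cannot be used. The other is that the number of sites is the whole cause: the identity link with rare events and several covariates is a problem in its own right.

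The same specification carries over to the binary secondary outcomes, some of which, such as VTE-related death, must be rarer than the primary composite that contains them. The pointer to 6.2 instead of 6.4.1 is an editorial slip and adds no weight.

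**What to change.** In 13.2.1, replace the identity-link model with one prespecified estimator:

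- **Estimator:** the marginal (standardised) risk difference from a logistic model with treatment and the patient-level minimisation factors (age band, cancer, COVID-19, SSPE type, previous bleeding), without site, with a delta-method or bootstrap 95% interval. Choose one interval method in the text.
- **Fallback:** if that model does not converge, the unadjusted risk difference with a Miettinen-Nurminen score interval.
- **Decision rule:** state that the upper limit of this interval is compared with 2.5%.
- **Scope:** apply the same rule to the risk differences for binary secondary outcomes in 13.2.2.
- **Editorial:** change the references to the minimisation list from 6.2 to 6.4.1 throughout section 13.2.

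The cost is wording in the protocol, carried into the SAP. The one statistical downside is small: site is a minimisation factor left out of the risk-difference model, so the interval may be slightly conservative.
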